6.3.2 Packaging

The sponsor or designee will provide the IP for this study. The IP is packaged in the following labeled containers:

- Volixibat 5 mg capsules
- Volixibat 10 mg capsules
- Volixibat 20 mg capsules
- Volixibat PBO capsules

6.3.3 Storage

The investigator has overall responsibility for ensuring that the IP is stored in a secure, limited-access location. Limited responsibility may be delegated to the pharmacy or member of the study team, but this delegation must be documented.

IPs are distributed by the pharmacy or designated member of the study team. The pharmacist/nominated team member will enter the unique subject identifier on the IP labels as they are distributed.

All IP must be stored at the clinic at 20 - 25°C (68 - 77°F); excursions are allowed between 15 - 30°C (59 - 86°F).

IPs must be stored in accordance with labeled storage conditions. Temperature monitoring is required at the storage location to ensure that the IP is maintained within an established temperature range. The investigator is responsible for ensuring that the temperature is monitored throughout the duration of the study and that records are maintained; the temperature should be monitored continuously by using either an in-house system, a mechanical recording device such as a calibrated chart recorder, or by manual means, such that both minimum and maximum thermometric values over a specific time period can be recorded and retrieved as required. Such a device (ie, certified min/max thermometer) would require manual resetting upon each recording. The sponsor must be notified immediately upon discovery of any excursion below 15°C (59°F) or above 30°C (86°F); these excursions will require site investigation as to cause and remediation. The sponsor will determine the ultimate impact of excursions on the IP and will provide supportive documentation as necessary. Under no circumstances should the product be

dispensed to subjects until the impact has been determined and the product is deemed appropriate for use by the sponsor.

The sponsor should be notified immediately if there are any changes to the storage area of the IP that could affect the integrity of the product(s), eg, fumigation of a storage room or a change in storage location.

6.4 Drug Accountability

Investigators will be provided with sufficient amounts of the IP to carry out this protocol for the agreed number of subjects. The investigator or designee will acknowledge receipt of the IP, documenting shipment content and condition. Accurate records of all IP dispensed, used, returned, and/or destroyed must be maintained as detailed further in this section.

The investigator has overall responsibility for administering/dispensing the IP. Where permissible, tasks may be delegated to a qualified designee (eg, a pharmacist) who is adequately trained in the protocol and who works under the direct supervision of the investigator. This delegation must be documented in the applicable study delegation of authority form.

The investigator or his/her designee (as documented by the investigator in the applicable study delegation of authority form) will dispense the IP only to subjects included in this study following the procedures set out in the study protocol. Each subject will be given only the IP carrying his/her treatment assignment. All dispensed IP will be documented on the eCRFs and/or other IP record. The investigator is responsible to ensure the retrieval of all study supplies from subjects.

No IP stock or returned inventory from a Shire-sponsored study may be removed from the site where originally shipped without prior knowledge and consent by the sponsor. If such transfer is authorized by the sponsor, all applicable local, state, and national laws must be adhered to for the transfer.

The sponsor or its representatives must be permitted access to review the supplies storage and distribution procedures and records. The site must ensure that the accountability and destruction records are complete, accurate, and ready for verification at each monitoring visit.

The process for return and destruction of IP must be determined and documented during the study start-up phase.

With the written agreement by the sponsor of the site's IP destruction procedures, all unused stock, subject returned IP, and empty/used IP packaging may be destroyed at the site or a local facility on an ongoing basis throughout the study and at the end of the study following verification of accountability by the CRA/study monitor. In this case, destruction records identifying what was destroyed, when, how, and by whom, must be obtained with copies provided to the sponsor. Destruction of IP must be in accordance with local, state, and national laws.

Alternatively, in the absence of written agreement by the sponsor of the site's IP destruction procedures, all unused stock, subject-returned IP, and empty/used IP packaging may be required to be sent to a nominated contractor on behalf of the sponsor for IP destruction on an ongoing basis throughout the study and at the end of the study. IP being returned to the sponsor's designated contractors also must be counted and verified by clinical site personnel and the CRA/study monitor. For unused supplies where the original supplied tamper-evident feature is verified as intact, the tamper-evident feature must not be broken and the labeled amount is to be documented in lieu of counting. Shipment return forms, when used, must be signed prior to shipment from the site. Validated electronic return systems (ie, IRT) do not require a shipment form. Returned IP must be packed in a tamper-evident manner to ensure product integrity. Contact the sponsor for authorization to return any IP prior to shipment. Shipment of all returned IP must comply with local, state, and national laws.

6.5 Subject Compliance

Subjects must be instructed to bring their unused IP and empty/used IP packaging to every visit. Drug accountability must be assessed at the container/packaging level for unused IP that is contained within the original tamper-evident sealed container (eg, blister pack) or at the individual count level for opened containers/packaging. The pharmacist/nominated person will record details on the drug accountability form.

7 STUDY PROCEDURES

7.1 Study Schedule

This study will consist of a screening period of up to 70 days (the screening period may be minimally extended under special circumstances only with the explicit approval of the Shire study physician), a 48-week Treatment period, and a Follow-up visit 4 weeks after treatment ends. A detailed display of all study procedures is provided in [Table 1](#).

Patients will be assessed according to the following schedule:

- Screening – Visit 1 (Weeks -10 to 0 [Day -70 to Day -1])
- Baseline – Visit 2 (Week 0 [Day 0])
- Treatment and Assessments – Visits 3 through 9 (Week 2 through Week 48)
- Follow-up – Visit 10 (Week 52, 4 weeks after completion of dosing)

7.1.1 Screening (Visit 1)

Screening procedures must be completed within 70 days prior to randomization for the first dose of the IP. The screening period may be minimally extended under special circumstances only with the explicit approval of the Shire study physician. At the screening visit, considered Visit 1 (Week -10 to 0, Day -70 to -1), all screening assessments and procedures are to be performed by the principal investigator or a qualified designee. See [Table 1](#) for a complete list of screening procedures to be performed.

Written, signed, and dated informed consent from the subject prior to the performance of any study-related procedures must be obtained by the principal investigator or a designee. A copy of the signed informed consent form must be given to the subject for their records.

The following screening procedures should be assessed at the beginning of the visit window, preferably between Day -70 and Day -49: inclusion/exclusion criteria, collection of subject information (demographics, medical and medication history AEs, and concomitant medications), a physical examination including vital signs, height, weight, and waist/hip measurements; collection of blood and urine samples for screening and safety assessments, performance of an electrocardiogram (ECG), and scheduling of MRI and liver biopsy. MRI and liver biopsy (if one has not been completed in the previous 6 months) should be performed with sufficient time to ensure results are received prior to the baseline visit.

A screen failure is a subject who has given informed consent and failed to meet the inclusion and/or met at least 1 of the exclusion criteria and has not been randomized or administered the IP. A subject who had been designated a screen failure may be re-screened up to one time. However, re-screened subjects must begin the screening procedure again, must be re-consented, and will be assigned a new subject number. Additionally, a subject's abnormal screening lab results may be repeated once for confirmation before designating a subject as a screen failure.

An investigative site may provide additional liver biopsy tissue to the central reader to be evaluated when the following criteria are met: 1.) the subject qualifies for the study on all inclusion/exclusion parameters except for liver histology, and 2.) the investigator's clinical assessment of the subject's local liver histology differs from that of the centrally read results, and 3.) the request to provide more tissue to the central reader for a second read must be requested before the patient is declared a screen failure. Any additional tissue samples provided must be read by the central reader and the central reader determines the final histological assessment.

7.1.2 Baseline (Visit 2)

Following the screening visit, subjects will return to the clinic within 70 days for Visit 2, (considered Week 0, Day 0), for baseline assessments including review of the inclusion/exclusion criteria, adverse events, and concomitant medications; physical examination with vital signs, weight, and waist/hip measurements; ECG; collection of blood and urine samples; stool assessment; and completion of the patient-reported outcome (PRO) EuroQol-5 Dimension-5 Level Questionnaire (EQ-5D-5L) survey. After completion of these assessments, subjects are randomized using Interactive Response Technology (IRT) to 1 of 4 treatment arms receiving volixibat 5 mg, 10 mg, or 20 mg, or PBO before the IA and then to 1 of the remaining arms after the IA. The initial supply of study drug is dispensed to ensure adequate daily dosing until the next scheduled study visit.

7.1.3 Treatment and Assessment Period (Visits 3 through 9/EOS)

During the 48 weeks of double-blind treatment, 7 clinic visits are scheduled to occur as follows:

- Visit 3 - Week 2, Day 14 (+/- 3 days)
- Visit 4 - Week 4, Day 28 (+/- 3 days)
- Visit 5 - Week 8, Day 56 (+/- 5 days)
- Visit 6 - Week 12, Day 84 (+/- 5 days)
- Visit 7 - Week 24, Day 168 (+/- 7 days) – Interim Analysis
- Visit 8 - Week 36, Day 252 (+/- 7 days)
- Visit 9 - Week 48, Day 336 (+/- 7 days) – End of Study

Subjects are reminded not to eat and not to take their study drug on the day of scheduled study visits prior to completion of assessments. They should bring their study drug with them to the visit. IP should be taken 30 minutes prior to the first meal of the day containing approximately 10-20 grams of fat.

The Schedule of Assessments provided in [Table 1](#) details the procedures to be completed at each visit. All Treatment visits (3 through 9) will include weight and waist/hip measurements, assessment of vital signs, and blood sampling for completion of biochemistry, hematology, serum glucose, lipid panel, HbA1c, and serum liver-related blood tests. At all visits, adverse events, and concomitant medications will be collected for all subjects, and female subjects of childbearing potential will have a urine pregnancy test. Subjects will return containers of unused study drug for assessment of accountability and compliance which will be documented in the IRT. New supplies of study drug will be dispensed at Visits 3 through 8.

Additional assessments will also occur less frequently during the Treatment Period for vitamin A, vitamin D, vitamin E, vitamin K via PT/INR, insulin, thyroid testing, urinalysis, ECG, physical examinations, stool assessment, and completion of the EQ-5D-5L.

An MRI will be repeated at Visit 7 for the 24-week IA and at Visit 9 (Week 48) for all subjects. A final liver biopsy will be performed at Visit 9 (Week 48) for all subjects unless a subject discontinues prior to Week 44, in which case the EOS liver biopsy is not required.

Sites that have supplied local slides for central reading for subject eligibility at Screening must also provide local liver histology slides for the subject to be centrally read for the Week 48 EOS liver biopsy. The central reader will provide the final liver histology assessment for Week 48.

7.1.4 Follow-up (Visit 10)

The follow-up period for this protocol is 4 weeks after the last dose of study drug with a final Follow-up visit scheduled for Week 52. Procedures to be completed at this final visit include physical examination, weight, waist/hip measurements, vital signs, samples for biochemistry and hematology, serum glucose, lipid panel, HbA1c, serum liver-related blood tests, insulin, thyroid

testing, stool assessment, and urine pregnancy test (for women of childbearing potential). Adverse events and concomitant medications will be recorded. All AEs and SAEs that are not resolved at the time of this contact will be followed to closure (see Section 8.1).

7.1.5 Additional Care of Subjects after the Study

No after care is planned for this study.

7.2 Study Evaluations and Procedures

All assessments and procedures are to be performed by the Investigator or a qualified designee who has been trained in the protocol. Assessments are to be performed according to the schedules shown in [Table 1](#). If a subject terminates the study early, the CRC will make reasonable effort to perform the EOS and safety follow-up assessments and procedures for the subject's safety and well-being.

7.2.1 Demographic and Other Baseline Characteristics

Demographic details will be obtained at screening and recorded on the eCRF. Data collected will include age, gender, ethnicity, height, and weight.

7.2.2 Efficacy

7.2.2.1 Liver Biopsy

Liver biopsies will provide histologic data for confirmation of the diagnosis of NASH, assessment and grading of NASH activity, and scoring of steatosis, lobular inflammation, ballooning, as well as fibrosis and additional features (see [Appendix 2](#) and Laboratory Manual for additional information).

7.2.2.2 MRI

The presence of $\geq 5\%$ steatosis on screening MRI from a centrally read radiologist will be performed either during the screening period or within 6 months prior to the first visit. Steatosis is assessed by MRI hepatic fat fraction. The Week 24 MRI will be conducted for subjects in the IA set only.

7.2.3 Safety

7.2.3.1 Medical History and Medications

Medical history including important medical events and concomitant medication and illnesses will be obtained at screening and will be recorded on the eCRF. Any existing medical condition present prior to the time of randomization should be reported as medical history

7.2.3.2 Physical Examination

A complete physical examination will be performed with a thorough review of body systems at screening, baseline prior to randomization, and at study visits specified in [Table 1](#). Physical

examinations will include a review of the subject's general appearance, as well as evaluation of the body systems including:

- Eyes, ears, nose, throat
- Lymph nodes
- Cardiovascular
- Skin
- Abdomen
- Neurological
- Spine and extremities

Abnormalities identified at the screening visit (Visit 1) will be documented in the subject's source documents and on the medical history eCRF. Changes after the screening visit (Visit 1) will be captured as AEs on the AE eCRF page, if deemed clinically significant by the investigator.

Height will be measured at the screening visit only while weight and waist and hip circumference will be recorded at all study visits. BMI will be calculated programmatically.

7.2.3.3 Adverse Event Collection

At each study visit, subjects will be questioned in a general way to ascertain if AEs have occurred since the previous visit (eg, "Have you had any health problems since your last visit?"). Adverse events are collected from the time informed consent is signed. (Please refer to Section 8, Adverse and Serious Adverse Events Assessment.)

7.2.3.4 Vital Signs

Vital signs include oral, temporal, or tympanic temperature, sitting blood pressure, pulse, and respiratory rate. Blood pressure should be determined by cuff (using the same method, the same arm, and in the same position throughout the study). Any deviations from baseline (Visit 2) vital signs which are deemed clinically significant in the opinion of the investigator are to be recorded as an AE.

7.2.3.5 Clinical Laboratory Evaluations

All clinical laboratory assays will be performed according to the central laboratory's normal procedures. Reference ranges supplied by the central laboratory will be used to assess the clinical laboratory data for clinical significance and out-of-range pathological changes. The investigator should assess out-of-range clinical laboratory values for clinical significance, indicating if the value(s) is/are not clinically significant or clinically significant. Clinically significant findings should be evaluated for recording as adverse events on the eCRF. Abnormal clinical laboratory values, which are unexpected or not explained by the subject's clinical

condition, may, at the discretion of the investigator or sponsor, be repeated as soon as possible until confirmed, explained, or resolved.

The following clinical laboratory assessments will be performed:

Biochemistry

- Albumin (ALB)
- Alkaline phosphatase (ALP)
- Alanine aminotransferase (ALT; SGPT)
- Aspartate aminotransferase (AST; SGOT)
- Blood urea nitrogen (BUN)
- C4
- Calcium (Ca)
- Bicarbonate (CO₂)
- Chloride (Cl)
- Creatinine
- Creatine kinase
- Gamma glutamyl transferase (GGT)
- Glucose
- Lactate dehydrogenase (LDH)
- Magnesium (Mg)
- Phosphate (P)
- Potassium (K)
- Sodium (Na)
- Total and direct bilirubin
- Total cholesterol
- Protein
- Triiodothyronine (T₃)
- Thyroid-stimulating hormone (TSH)
- Triglycerides
- Uric acid

Hematology

- Hemoglobin
- Hematocrit
- Mean corpuscular hemoglobin (MCH)
- Mean corpuscular volume (MCV)
- Platelets
- Red blood cell (RBC)
- White blood cell (WBC) count with differential
- Prothrombin time (PT)
- Activated partial thromboplastin time (aPTT)
- International normalized ratio (INR)

Urinalysis

- Appearance (clarity and color)
- Bilirubin
- Blood
- Glucose
- Ketones
- Leukocyte esterase
- Microscopic examination of sediment
- Nitrite
- pH
- Protein
- Specific gravity
- Urobilinogen
- Oxalate

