One of the factors contributing to the pathogenesis of NASH is abnormal cholesterol metabolism and the accumulation of free cholesterol in the liver. The free cholesterol is directly toxic to hepatocytes, which leads to inflammation and fibrosis (Musso et al., 2013). One treatment approach is to remove the cholesterol from the liver to decrease and possibly reverse the damage to the hepatocytes. This is one of the mechanisms by which SHP626 will treat NASH.

Due to the mechanism of action (MOA), volixibat is under development for the treatment of NASH and may also be able to improve the metabolic syndrome that is associated with NASH. Volixibat inhibits ASBT therefore BAs are excreted in the feces and this loss forces the liver to synthesize new BA which utilizes cholesterol in the liver and serum. Volixibat also has the potential to reduce IR, which is considered to be the most common underlying risk factor for the development of NASH (Pagano et al., 2002; Sanyal et al., 2001).

Volixibat was initially being evaluated for its use as an intervention for dyslipidemia. As a result of initial observations in animals that serum low-density lipoprotein cholesterol (LDL-C) and total liver cholesterol content could be decreased after administration of volixibat, additional work was undertaken to support the safety and tolerability of the drug in healthy volunteers. Clinical and non-clinical studies have demonstrated very low systemic exposure across species.

Oral administration of volixibat at doses up to 300 mg once daily and 50 mg administered daily for 14 days to healthy male subjects was generally safe. A Phase 1 study revealed that volixibat is tolerated at the 10 mg dose for 28 days and that there were trends towards increasing high-density lipoprotein cholesterol (HDL-C), decreasing LDL-C, and decreasing fasting glucose in patients with T2DM (LUM002-101 trial).

A healthy volunteer study investigating 12 days of varying levels of repeat doses of volixibat has provided key pharmacodynamic information for dose selection as measured by the effect of volixibat on excreted fecal bile acid (FBA) levels (SHP626-101). In addition, the study investigated safety and tolerability over the dose range that was considered for this Phase 2 study.

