2.2.3 Exploratory Objectives

- To explore the effect of volixibat compared to PBO on liver histology (measured by individual SAF scoring components: Steatosis (S), Activity (A), and Fibrosis (F))
- To explore the effect of volixibat compared to PBO on anthropometric measures (body weight, body mass index (BMI), waist circumference and waist-hip ratio)
- To explore the effect of volixibat compared to PBO on homeostasis model assessment-IR (HOMA-IR) and HOMA-beta cell function (HOMA-%B) in subjects with T2DM
- To explore the effect of volixibat compared to PBO on BA synthesis (7-alpha-hydroxy-4-cholesten-3-one [C4])
- To explore the effect of volixibat on patient-reported health-related quality of life (HRQoL) and overall health status.

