7.2.3.6 Additional Laboratory Assessments

Laboratory samples will be collected and assessed for:

- HIV testing and assessment of Hepatitis B/C including HBcAb, HBsAg, HBVDNA, and HCVAb (if HCVAb is positive an HCVRNA will be performed) will occur at the screening visit only
- Lipid panel including fasting total cholesterol, HDL-C, LDL-C, and triglycerides at each scheduled study visit (Visits 1 through 10)
- HbA1c will be tested at every scheduled visit (Visits 1 through 10)
- Full coagulation panel will be done at screening and baseline, but only PT/INR is required at remaining time points at Visits 4, 7, and 9
- Insulin will be tested at screening, baseline, at Visit 4 and Visits 6 through 10
- HOMA-IR and HOMA-%B: will be calculated programmatically from serum glucose tested at screening, baseline, Visits 7, 9, and 10
- Vitamin A, Vitamin D, Vitamin E, and Vitamin K (via PT/INR) will be tested at baseline, and Visits 4, 7, and 9.
- Thyroid testing including TSH and T3 will be tested at screening, baseline, and Visits 4, 6, 7, 9, and 10
- C4 samples will be collected at baseline and Visits 6, 7, 9, and 10

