9.3 Data Handling Considerations

Data that may potentially unblind the treatment assignment (eg, treatment allocation, and IP preparation/accountability data) will be handled with special care during the data cleaning and review process. These data will be handled in such a way that, prior to unblinding, any data that may unblind study team personnel will be presented as blinded information or otherwise will not be made available. If applicable, unblinded data may be made available to quality assurance representatives for the purposes of conducting independent drug audits.

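### C4, the trial's marker of drug action, sits in the site-reviewed biochemistry list with no rule withholding on-treatment results from blinded investigators

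*Protocol*

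**What the plan says.** Section 7.2.3.5 (Clinical Laboratory Evaluations) introduces its panels with "The following clinical laboratory assessments will be performed". C4 is the sixth item under Biochemistry, between blood urea nitrogen and calcium. The same section states that "Reference ranges supplied by the central laboratory will be used to assess the clinical laboratory data for clinical significance and out-of-range pathological changes" and that "The investigator should assess out-of-range clinical laboratory values for clinical significance". Clinically significant findings are then considered for recording as adverse events, and unexplained abnormal values may be repeated. C4 is not excepted from any of this.

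Section 7.2.3.6 gives the timing: "C4 samples will be collected at baseline and Visits 6, 7, 9, and 10". In Table 1 C4 has a row of its own, separate from the biochemistry and hematology row.

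Section 1.2 describes the mechanism: "Volixibat inhibits ASBT therefore BAs are excreted in the feces and this loss forces the liver to synthesize new BA". Section 2.2.3 names C4 as the measure of bile acid synthesis in an exploratory objective.

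The only text on masking potentially revealing data is Section 9.3: "Data that may potentially unblind the treatment assignment (eg, treatment allocation, and IP preparation/accountability data) will be handled with special care". That handling belongs to data cleaning and review, and the people it shields are study team personnel.

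**The concern.** C4 is not an ordinary safety analyte in this trial. It is the laboratory readout of what the drug is meant to do. If post-baseline values reach the site with the rest of the biochemistry, an investigator can compare a subject's on-treatment value with the same subject's baseline and form a view on whether that subject is on volixibat.

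The investigator then makes decisions that such a view could colour. He or she judges whether each adverse event is related to treatment (Section 8.1.2). Related deaths, or two similar related serious events, trigger an urgent safety review (Section 4.5.4). The investigator may also withdraw a subject (Section 4.5), and discontinuations due to adverse events form the tolerability comparison that can lead to a dose being dropped at the interim analysis (Section 9.5.1).

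**Working it through.** No power, alpha or sample size enters here, so the check is a reading of the passages against one another, with a little arithmetic on the schedule.

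1. **Is C4 inside the investigator's review duty?** Yes, on the text. It is in the Biochemistry list of Section 7.2.3.5, and the duty in that section covers out-of-range clinical laboratory values generally. The duty is worded as something the investigator should do. It takes effect for C4 only if the central laboratory supplies a C4 reference range; the protocol gives none.

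2. **Does C4 carry information about treatment?** On the protocol's own reasoning, yes. Section 1.2 says bile acid loss under volixibat forces new synthesis, and Section 2.2.3 uses C4 to measure synthesis. This supports an average shift on active drug. It does not say how well one subject's value separates the arms.

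3. **Do results arise while the subject is still blinded?** Visits 6, 7, 9 and 10 are Weeks 12, 24, 48 and 52, and treatment lasts 48 weeks.
   - Week 12 result: 48 − 12 = 36 weeks of blinded treatment remain.
   - Week 24 result: 48 − 24 = 24 weeks remain.
   - Weeks 48 and 52 fall at or after the end of treatment.

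   Two on-treatment results therefore precede the end of dosing. Both also precede Week 44, before which a discontinuing subject is not required to have the final biopsy (Sections 4.5 and 7.1.3), by 44 − 12 = 32 and 44 − 24 = 20 weeks.

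4. **How much could be guessed without C4?** With 1:1:1:1 allocation before the interim analysis, the chance of being on active drug is 3/4. With equal allocation afterwards it is 2/3 if two doses continue and 1/2 if one does. How far a C4 result moves these figures needs its mean, spread and effect size, none of which is given.

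5. **Does any passage keep C4 from sites?** No. Section 9.3 opens its list with an eg, so C4 could fall under its general rule, but that rule shields study team personnel. It does not address a laboratory report sent to an investigator.

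6. **Which outcomes are within reach?**
   - Causality and adverse event recording: directly, because the investigator makes those judgments.
   - Interim tolerability: through discontinuations. For events before a subject's Week 24 visit, only the Week 12 result can have played a part.
   - Primary endpoint: only indirectly. A discontinuation before Week 44 usually means no biopsy, and missing data count as non-response (Section 9.8.1). The histology itself is read centrally.

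7. **Does anyone at the site need C4?** No eligibility criterion, withdrawal criterion or stopping rule uses it, and neither Appendix 4 nor Appendix 5 mentions it.

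**The case against.** The strongest reply is that the protocol never says C4 results are sent to sites. Section 7.2.3.5 may be only an inventory of assays. C4 has its own row in Table 1 and its own line in Section 7.2.3.6, and the content of site reports may be set in a laboratory manual that is not at hand. This stands as a limit: C4 may in practice be suppressed. But such a setting would depart from Section 7.2.3.5 as written, which puts C4 among the results for investigator review.

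A second reply is that sites already see other signals. Lipids are measured at every visit, and gastrointestinal events generally rose with dose in Phase 1 (Section 1.3). That is fair, and what C4 adds to them is not known. The difference is that investigators need adverse events for safety, and no safety rule needs C4.

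Third, many gastrointestinal discontinuations may come before Week 12, since Section 1.3 says these events generally diminished with continued treatment. That reduces the part C4 can play in the interim comparison without removing it.

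A reader might go further and infer that the quality-of-life results are compromised. The documents do not support this: the EQ-5D-5L is completed by the subject, and no passage describes C4 results being given to subjects.

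**Conclusion.** The point holds as an avoidable weakness in blinding. Followed as written, Section 7.2.3.5 puts a marker of the drug's mechanism before blinded investigators at Weeks 12 and 24, and no passage withholds it. The size is unknown: with no C4 effect, spread or range, the share of subjects who could be identified cannot be computed. The conclusion assumes that the central laboratory reports C4 to sites as it does the other listed biochemistry, and that the shift on active drug is large enough to notice in some subjects.

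The exposure lies mainly in causality and adverse event judgments and discontinuation decisions. Through discontinuations it reaches the interim tolerability comparison, chiefly by way of the Week 12 result. A reader might infer that C4 reliably reveals the arm, or that the primary endpoint is directly biased. Neither follows. The first needs data that the documents lack. The second needs an investigator to guess the arm and then let the guess affect whether the subject stops treatment, because the biopsy reading is central.

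**What to change.** - **Section 7.2.3.5:** take C4 out of the site-reviewed Biochemistry list. Keep the sampling in Section 7.2.3.6 and Table 1 unchanged.
- **Section 7.2.3.6:** state that post-baseline C4 results are not released to sites or to the blinded study team until database lock.
- **Section 9.3:** name C4 as potentially unblinding data, and extend the section to investigators and site staff.

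No special route to the Data Monitoring Committee's statistician is needed: the efficacy measures in Section 9.5.1 are MRI-PDFF and ALT, and no passage gives the committee a use for C4.

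The cost is a reporting setting at the central laboratory and a few sentences. The exploratory objective keeps all its data, and no safety rule loses an input. If the laboratory already suppresses C4, the change only brings the protocol into line with practice.
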